B3b1. Design. A cluster-randomized clinical trial design will be used in which 36 group homes (14 male, 14 female, and 8 co-ed) will be randomly assigned to either the STEPS intervention (n = 18; 7 male, 7 female, and 4 co-ed homes) or attention-control (n = 18; 7 male, 7 female, and 4 co-ed homes). We have worked with or are currently working with eight agencies, five of which were in the original nine that were randomly ordered for participation. Two more of the original nine requested to be contacted again in early 2019, related to absence of key staff for one and merger with another agency for the other. Within some agencies, we will be able to identify six homes (2 of each gender and 2 co-ed) that meet criteria. Within agencies with only 3 homes for any or all three genders (male, female, co-ed) we will randomize homes within gender. If recruitment rates render a randomized home ineligible, we will randomly select an alternative home from a different agency. For agencies with only 1 eligible home for any gender, we will draw additional homes from a different agency. Whenever possible, we will adjust ordering of agencies to allow all participating homes within an agency to participate within the same time frame so that they are part of the same cohort. In addition, we may need to recruit additional agencies in order to reach the required number of 36 homes for this research. We will inform the IRB of any new agencies and provide letters of support. Group homes (residents and staff) will be recruited after randomization to simplify the process of explaining the study to individuals with ID. If fewer than two residential staff and/or fewer than three residents are willing to consent to participation, that group home will be ineligible and the third group home serving the same gender within that agency will be approached for recruitment.

Group homes in both conditions will receive one session (STEPS or attention-control Food for Life) every other week for 12 weeks, for six total sessions, and a booster at 18 weeks. Data collection for both conditions will be at baseline (pre-intervention) and 12 weeks (post-intervention), to estimate intervention effects and at 24 and 36 weeks after the start of the intervention to estimate maintenance.

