Prior to going on pause related to COVID 19 on March 12, 2020 We had already finished or begun the intervention at 25 homes homes (8 female and 15 male, and 2 co-ed). These include 17 homes with 24-week data collection, 5 with 12-week data collection, 4 that were part way through the intervention. There are an additional 2 homes where we had all consents and completed baseline data collection, but had not started the intervention (both co-ed), and 7 homes where we had started the consent process (3 female, 4 co-ed). Starting in study Week 204 (Month 11 of Year 4), we will again recruit two cohorts of five to six group homes (plan for two male, two female, and 1-2 co-ed home for each condition), staggered to begin every 10-12 weeks over weeks 204-260. There will be eight weeks of recruitment for each cohort of five- six homes (allowing time to contact guardians if needed). We plan to return to the homes where we had consents but had not completed the consent process or had not started the intervention and work to recruit these homes again. The COVID pandemic has led to efforts to improve online learning for this population http://project10.info/DPage.php?ID=428). Internet-based technology has been found to be feasible among persons with ID for more than 10 years (Lotan et al., 2009). We now will conduct the intervention virtually. Data will be collected using an intent-to-treat approach; thus, we will attempt to collect data from subjects even if they stop attending groups.

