be used to update training of staff and prevent drift. **Receipt** of the seven sessions, or dose, will be **Procedures**. Baseline data collection: The time needed for administration of questionnaires and videotape (baseline, 12 weeks, and 24 weeks) is estimated at 1 hour 40 minutes for individuals with ID, and 25-40 minutes for the residential staff. Based on our pilot study, the attention of individuals with ID can be held for approximately 50 minutes. Therefore, data collection for individuals with ID will be broken into two sessions. Also, participants will be given breaks as desired. During the first data collection session, For the data collection, research team members will work with residential staff to find a private, quiet place in the homes and to get assistance from staff if needed. All of the measures will be administered via Webex. Responses to the GDS will be recorded in REDCap. For the PST, the data collector will read the vignette to the resident being interviewed and record the response using the audio only function in Webex. Data collection for residential staff members will be conducted at their convenience over the phone or virtually. Answers will be entered into REDCap. 12- and 24-week data collection: will use the same procedures as at baseline data collection the questionnaires and audiotapes of the Problem-solving Task (PST)⁴² will be completed. Self-report questionnaires will be read to each individual with ID and will be done over Webex with the participant in a private, quiet place in the homes. For the PST, the data collector will read the vignette to the resident being interviewed and audiotape the response using the audio only record function in Webex.. A second data collection visit will be arranged to obtain the digital recording of the entire group that will be used to score the IFIRS. 62,73 For the IFIRS, the data collector will meet with the group over Webex and help the group generate the topic for discussion. The group of individuals with ID and their staff will discuss the problem. The discussion with be recorded with the webcam video function in Webex. Data collection for residential staff members will be conducted at their convenience via phone or Webex. The Webex recorded videos will be made available for secure download by [name] laboratory at Iowa State University (Ames, IA) to be scored by her specialists.

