Specific Aim 1. Because multiple dependent variables are being examined, a repeated-measures multivariate analysis of variance will be conducted to ensure control of experiment-wise α , and to perform an initial assessment of intervention effects. We will then calculate intervention efficacy on individual measures of SPS skills and A/CBs of individuals with ID using a nested hierarchical model; the three levels will be group home, person within site, and time-point within person. All analyses will be performed on an intent-to-treat basis. Intervention condition will be dummy coded (treatment vs. control) at the level of the group home. To control for effects of background characteristics on the intervention, measures associated with background variables will be entered into the model as two propensity measures: one based on individual measures, the other based on group home measures. This is, in effect, a two-level propensity analysis. This two-level approach is a novel and innovative statistical method for conducting propensity analysis. Propensity analysis is a well-validated statistical approach useful in balancing groups on observed covariates so that analyses of treatment effects are more accurate. 88,89 If a propensity measure has a nonsignificant effect, it will be discarded; if significant, it will be included in the final model. Categorical covariates (e.g., gender, ethnicity) will be dummy-coded and entered into the model as a block. Propensity scores will be estimated using individual participant (e.g., age, length of residence) and group home level measures (e.g. location [urban/suburban], gender, and number of residents/home) that could influence outcomes. We also will check for differences in baseline SPS and A/CBs by agency and by interventionist; if found, we will enter these into the propensity score analysis. This final set of variables (the direct predictors) will constitute an optimal model for assessing each outcome measure.

Specific Aim 2. We expect the support environment for SPS (residential staff SPS, group SPS, and group cohesiveness) to mediate improvements that occur in the individuals with ID. To assess the mediating effects, we

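### Delivery and interview- or video-based measurement moved to Webex after the March 2020 pause, but the Aim 1 model has no term for mode or period

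*Combined protocol and SAP*

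**What the plan says.** Section B3b1 (Design) plans 36 homes, 18 per arm. It reports the pause on 12 March 2020, by which time "We had already finished or begun the intervention at 25 homes". It gives their status as "17 homes with 24-week data collection, 5 with 12-week data collection, 4 that were part way through the intervention". There were also "an additional 2 homes where we had all consents and completed baseline data collection, but had not started the intervention". Delivery then changes: "We now will conduct the intervention virtually". The Procedures section and B3b7 change measurement too: "All of the measures will be administered via Webex". The PST is read and recorded over Webex, and the group discussion scored for the IFIRS becomes a webcam recording.

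The two fidelity sections require data collectors to be retrained before virtual data collection begins, and B3b6 requires the same of interventionists before virtual sessions. The earlier phase was therefore not virtual.

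The Aim 1 model in B3b8 is hierarchical: "the three levels will be group home, person within site, and time-point within person". Its named terms are condition, an individual-level and a home-level propensity measure, and agency or interventionist if baseline differences are found. A propensity measure that is not significant is dropped. Neither B3b8 nor the list of potential problems in B3b9 mentions mode, period or cohort.

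**The concern.** An additive mode shift does little harm in a home measured in one mode throughout: the home-level effect absorbs it, and change from baseline is untouched. The difficulty is a home whose baseline was in person and whose follow-up is virtual. There the shift is confounded with time and enters the home's change score. If the arms contain different numbers of such homes, part of the shift appears as treatment effect. If they contain equal numbers, the shift still adds unexplained variation between homes.

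Separately, 11 of 36 homes (31%) would receive wholly virtual delivery. The pooled effect then averages two delivery formats, and the analysis plan has no step to examine whether they differ.

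**Working it through.** The plan states no figure for a mode effect and gives no power calculation, ICC or SD, so there is nothing to reproduce. The check uses the home counts plus an assumed shift.

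**Counts (B3b1; Recruitment, consent, and retention)**
- Begun before the pause plus still to recruit: 25 + 11 = 36, which matches the design.
- Status of the begun homes: 17 + 5 + 4 = 26, against 25 stated. The gender split does add up: 8 + 15 + 2 = 25.
- Homes that could have virtual or post-pause data through week 24: 36 − 17 = 19 at most. Adding 5 + 4 + 11 gives 20, but 17 + 20 = 37 exceeds the design, so the discrepancy of one home carries through.

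**Which homes can straddle, by contrast**
- B3b1 uses baseline and 12 weeks to estimate intervention effects, and 24 and 36 weeks for maintenance.
- Baseline to 12 weeks: the 4 part-way homes, plus the 2 baseline-only homes if baseline is not repeated. The 5 homes with 12-week data had both time points before the pause.
- Baseline to 24 weeks: the 5 and the 4, so 9 interrupted homes (8 if the surplus home is among them), plus possibly the 2 baseline-only homes.

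**Bias**

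With 18 equally weighted homes per arm, bias in the arm difference in mean change = (difference between arms in number of straddling homes ÷ 18) × mode shift. The shift of .3 to .5 SD is an assumption, as is every split below.

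| Contrast | Split | Difference | Shift .3 SD | Shift .5 SD |
|---|---|---|---|---|
| 12 weeks | 2:2 | 0 | 0 | 0 |
| 12 weeks | 3:1 (or 4:2 of six) | 2 | 2/18 × .3 = .03 | 2/18 × .5 = .06 |
| 12 weeks | 4:0 | 4 | 4/18 × .3 = .07 | 4/18 × .5 = .11 |
| 24 weeks | 5:4 | 1 | 1/18 × .3 = .02 | 1/18 × .5 = .03 |
| 24 weeks | 6:3 | 3 | 3/18 × .3 = .05 | 3/18 × .5 = .08 |
| 24 weeks | 7:2 | 5 | 5/18 × .3 = .08 | 5/18 × .5 = .14 |

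**Could the covariates already named carry mode?** They are introduced as examples, so the list is not closed. A propensity score built from baseline characteristics still cannot represent a mode that changes between visits, and it may be discarded under the significance rule.

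**The case against.** The design already limits between-arm bias. Both arms go virtual and share data collectors. Homes are randomized within agency and gender, and homes from one agency are kept in one cohort where possible. Balance of the remaining homes by condition is already planned. All of this stands and makes a large imbalance less likely, but it does not guarantee balance among the few interrupted homes, whose arm split is not reported.

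Not every outcome changes mode. The GMI comes from agency staff and, per Table 3, records and work settings; incident reports are agency records. This also stands. For these outcomes the issue is calendar period, which affects both arms and biases the comparison only if the arms differ in exposure to it.

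Virtual follow-up of the interrupted homes is not documented. B3b1 says the team will return to homes where consent was incomplete or the intervention had not started; it is silent on the 5 and the 4. Their later data may be missing rather than virtual, in which case the multiple imputation in B3b8 applies and the problem is one of missing data. This stands, and is why the straddling counts are upper limits.

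A reader might infer that all 9 interrupted homes threaten the main intervention effect, with a bias up to .14 SD. The documents do not support that: the 5 homes with 12-week data can be affected only at 24 weeks or later. Nor is the switch concealed, since B3b1 describes it openly; what is missing is its handling in the analysis.

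**Conclusion.** The point holds as a gap in the model specification. Mode and period change mid-trial, and no stated term can represent a change between visits within a home. On the assumed shift of .3 to .5 SD, the 12-week effect could be biased by .03 to .06 SD for an arm difference of 2 straddling homes, from zero if balanced to .07 to .11 SD for a difference of 4. The 24-week range is about .02 to .14 SD for splits of 5:4 to 7:2. These figures rest on equally weighted homes, an assumed shift, unknown arm splits, and the interrupted homes having resumed virtually.

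The documents do not show that the treatment effect is in fact biased. They show that the planned analysis could neither detect nor remove such a bias. The change is worth making because it is cheap and should be fixed before the data are analysed.

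**What to change.** 1. For PST, IFIRS and questionnaire outcomes, add a time-varying fixed effect for assessment mode (in person or virtual) to the three-level model. Keep it whether or not it is significant.
2. For incident reports and GMI, add a term for before or after 12 March 2020.
3. Add a sensitivity analysis excluding homes that straddle the switch.
4. Report assessment mode by arm, and the condition-by-mode interaction as exploratory.
5. State whether the part-way and 12-week homes resumed virtually and whether baseline is repeated in the 2 baseline-only homes. Reconcile the status counts (26 against 25).

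The cost is about one degree of freedom per model plus the secondary analyses. Mode and date should be known for each assessment, so no new data are needed. There are two limits. Mode and pandemic period largely coincide, so the term cannot separate them. The interaction will be imprecise, since it rests largely on the 11 virtual homes and is tested at .01.

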Group home inclusion/exclusion criteria are: (1) serve individuals with mild to moderate ID; (2) have at least 10 A/CB incident reports in resident files over the prior six-month period, with at least 30% of residents in each home having incident reports in that period; (3) have 5 or more residents, with a minimum of 3 agreeing to participate; (4) individuals with ID and residential staff all speak English; and (5) have one residential staff member who agrees to participate. Group homes will be excluded if they serve individuals with ID who also have serious mental illness (e.g., severe autism, schizophrenia) or homes for forensic populations. Group homes that participated in the pilot study (B3a) will be excluded. Ten accredited agencies located across the Chicago area, managing over 225 group homes serving individuals with mild to moderate ID, have agreed to participate (see letters of support, Appendix A). Generally, agencies do not have their homes located closer than 1.5 miles to one another (Figure 4); eight of ten are included on the map. This geographic separation reduces contamination across sites.

Individuals with ID inclusion criteria are: (1) mild to moderate ID (operationalized as IQ 50-75⁶⁴ per agency records) and mild to moderate limitations in adaptive functioning (measured by the Inventory for Client and Agency Planning⁶⁵ used in all residential agencies in Illinois, per agency record); (2) live in a chosen group home; and (3) verbal and speak English. Individuals who participated in the pilot study (B3a) will be excluded.

Residential staff inclusion criteria are: (1) employed as residential staff in the chosen group homes and (2) speak and read English. Residential staff who do not meet these criteria or who participated in the pilot study (B3a) will be excluded.

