For individuals with ID who have a legal guardian, agencies will send the guardian a recruitment letter about the purpose of the study and eligibility. A research team member will call all legal guardians who express an interest to explain the study and answer questions. A consent form will be sent to the guardian. Guardian consent may be sent to us by mail, fax or email of scanned document. After guardian consent is obtained, a research team member will contact the potential participant by phone or Webex to explain the study, answer questions and explain that participation is voluntary. They will also answer questions and obtain assent from the individuals with ID. For individuals with ID who are their own guardians, an agency QIDP will read a flyer about the study and obtain agreement to be contacted. Once the recruitment flyer is returned (scanned document via email, fax, USPS), a research team member will contact the individual with ID via phone or Webex and determine best means to send the consent form. Materials can be brought by an agency staff person, sent via email, fax, or USPS. Once the individual with ID has the consent, the research team member will again contact the individual, explain the study, read the consent form over with the person, confirm eligibility, answer questions, and obtain consent and set up a means to have consent sent to research team. If the individual with ID prefers, a residential staff person can be

present for assistance. Participant consent may be sent to us by mail, fax or email of scanned document. Based on previous experience, we will use Fisher and Cea's⁶⁸ recommendations to assess ability of individuals with ID to consent/assent (Appendix B). Those unable to consent/assent will not be accepted.

Participating individuals with ID and staff in STEPS and attention-control Food for Life conditions will receive \$20 for each data collection assessment: baseline, 12, and 24 weeks. The interventionist or research assistant will contact participants who miss sessions to invite them to continue if they still wish.(see Human Subjects). We will maintain regular (at least every two weeks) contact with agency management staff to discuss progress and any concerns. (see Environment). Also, we have access to the Community Engagement Board of the Center for Clinical and Translational Science at the University of Illinois at Chicago for input on recruitment and retention (see Letters of Support).

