(4) Incident reports are filled out by residential staff who observe the incidents and reviewed by QIDPs. Bias in reporting by residential staff based on intervention condition is possible. The agencies, however, have protocols for reporting incidents, and, during orientation to the program, we will instruct residential staff to continue to use those protocols. Bias, if present, is more likely to impact reports of minor incidents (e.g., arguments) than reports of serious incidents (e.g., involving injury or property damage). By analyzing serious incidents separately, we will minimize bias in incident reports. We also have a second measure of behavior not dependent on residential staff report, the IFIRS Dyadic Interaction Scales. Finally, we are collecting data on A/CBs from work setting supervisors where informants will be naïve to study conditions. Though it is possible that IFIRS coders or work setting supervisors may become aware of study condition, this is expected to be rare and to have minimal impact on study results. (5) We have chosen to randomize prior to recruitment so that individuals with ID can be told specifics about the intervention to which they have been assigned. Although it would be ideal to randomize after recruitment and baseline data collection, trying to explain to individuals with ID that they may be assigned to either STEPS or a nutrition intervention would likely be confusing. (6). While we only have 3 measures related to nutrition among individuals with ID and one measure among residential staff, our study has a larger sample size participating in a nutrition intervention than previous studies, has a homogenous sample and defined randomization techniques. We expect to contribute to the body of research on nutrition interventions in this population.

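### Eligible residents are not fixed before homes are randomised, so the enrolled mix can differ by arm, and Aim 3 states no baseline adjustment to remove it

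*Combined protocol and SAP*

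**What the plan says.** Section B3b1 (Design) sets the unit of allocation: "36 group homes (14 male, 14 female, and 8 co-ed) will be randomly assigned". It also sets the order: "Group homes (residents and staff) will be recruited after randomization to simplify the process of explaining the study to individuals with ID". Section B3b9, item 5, gives the reason, which is to "randomize prior to recruitment so that individuals with ID can be told specifics about the intervention to which they have been assigned", and concedes the alternative: "Although it would be ideal to randomize after recruitment and baseline data collection".

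The resident criteria contain "2) live in a chosen group home; and (3) verbal and speak English" and attach no date to residence. A home needs five or more residents, of whom at least three must agree.

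Under Recruitment, consent, and retention, the agency makes first contact. It writes to the guardian where there is one. For residents who are their own guardian, "an agency QIDP will read a flyer about the study and obtain agreement to be contacted". The same group of professionals supplies the GMI scores (Procedures) and reviews incident reports (B3b9, item 4). Concealment of allocation is described for data collectors only (Fidelity plan).

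On analysis, B3b8 tests arm comparability on demographics, life events, environment and current health, with .01 used for all tests. Specific Aim 1 uses repeated measures with time-point nested in person, and discards a propensity measure that is not significant. Specific Aim 3 takes the number of A/CB incidents as its effectiveness measure and mentions no baseline adjustment.

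**The concern.** Once a home's programme is known, those making the approach have a natural reason to think of different residents. Someone with frequent incidents is an obvious candidate for a problem-solving programme and a less obvious one for a nutrition programme. Residents and guardians may also respond differently to the two offers. Outcomes are analysed in those who enrol, so randomising the homes does not by itself protect the comparison of enrolled residents.

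The stated reason, that describing two possible programmes would confuse residents, supports taking consent after randomisation. It does not require the list of eligible residents to stay open until then. That list can be drawn from IQ, adaptive-functioning and incident records that the agency already holds and uses for eligibility. Without it, the number of eligible residents never put forward cannot be stated for either arm.

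The analysis covers the gap only in part. The comparability tests do not name baseline A/CBs, a test at .01 will often pass a moderate imbalance, and a propensity term survives only if significant.

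**Working it through.** The plan states no figure on this point, so there is nothing to reproduce. The calculations below are illustrations; their assumptions are marked.

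**1. Effect of mix on incident levels (the Aim 3 case).** Assumptions: one third of residents have prior incidents (the home criterion requires at least 30%); their incident rate is 5 times that of the others; the others enrol at 85% in both arms (the pilot enrolled 12 of 14 = 86%). The enrolment rates for residents with incidents are also assumed. Share with prior incidents among those enrolled = (1/3 × p) / (1/3 × p + 2/3 × 0.85). Relative incidents per participant = 1 + 4 × share.

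- 90% in STEPS, 70% in control: shares 0.300/0.867 = 0.346 and 0.233/0.800 = 0.292. Levels 2.385 and 2.167. Ratio **1.10**.
- 95% in STEPS, 55% in control: shares 0.317/0.883 = 0.358 and 0.183/0.750 = 0.244. Levels 2.434 and 1.978. Ratio **1.23**.

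The ICER denominator is the difference in incidents between arms. With a ratio of 1.10, a true 10% reduction would appear as 0.90 × 1.10 = 0.99. With 1.23, a true 20% reduction would appear as 0.80 × 1.23 = 0.98. Either way the denominator is close to zero. Selection in the opposite direction would inflate the apparent benefit.

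**2. The same scenario in Aim 1.** If the rates are stable, the 1.10 or 1.23 ratio is already present at baseline and cancels in the ratio of change: 1.10/1.10 = 1. Table 3 schedules incident reports, GMI and IFIRS at week 0, so the data for this exist.

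**3. A continuous version.** Take 3 residents enrolled from a home of 5, 6 or 8, with behaviour standard normal. Complete selection in one arm only (mean of the 3 most extreme, by simulation) shifts baseline by 0.55, 0.70 or 0.92 SD. If selection correlates only 0.3 with behaviour, the shift is 0.17, 0.21 or 0.28 SD.

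- *Comparison of levels:* 18 homes per arm, two-sided α = 0.01 (sidedness assumed), m = 3 to 5 enrolled per home and ICC 0 to 0.2 (both assumed), SE = √[2(1 + (m − 1)ICC)/(18m)]. A shift of 0.17 SD raises the false-positive rate from 1% to about 3–8%; 0.28 SD raises it to about 9–24%.
- *Change from baseline:* with reliability 0.80 (the GMI test-retest value in Table 3), 20% of the shift remains through regression to the mean. Complete selection leaves 0.55 × 0.2 = 0.11 to 0.92 × 0.2 = 0.18 SD. The 0.3-correlation case leaves about 0.03 to 0.06 SD.

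**4. Move-ins.** At an assumed turnover of 5–15% a year, the eight-week recruitment window gives 8/52 × 5–15% = 0.8–2.3% of residents. For homes paused on March 12, 2020, if their allocation stands, the gap to the document date of April 8, 2021 is 56 weeks: 56/52 × 5–15% = 5–16%.

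**The case against.** The order of randomisation and recruitment is disclosed, with a reason specific to this population. The recruitment text is written by category of resident and can naturally be read as covering every guardian and every self-guardian resident. Homes are small, and the pilot enrolled 12 of 14. Participant tracking is to follow CONSORT, and week-0 data allow baseline imbalance among participants to be shown by arm. Baseline SPS and A/CBs are to be checked by agency and by interventionist; since each arm has its own interventionists, that could reveal an arm difference indirectly. Both arms receive an active programme.

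Most of this stands, and it limits the point. It does not close it: arm is not named in that check, what it finds goes into a propensity term that may be discarded, and CONSORT tracking cannot count residents never put forward if no list exists.

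Three stronger readings are tempting but not supported.

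- *A real reduction of 10–20% would be hidden in Aim 1.* Aim 1 uses baseline and repeated measures, so a stable difference in mix largely cancels (working, steps 2 and 3).
- *Enrolling more overweight residents in the nutrition arm would bias Aim 4.* Its weight and BMI hypothesis concerns improvement among overweight and obese individuals. A larger number of them in one arm does not by itself create a difference in improvement within that group.
- *Residents will be moved into homes because of the arm.* No passage describes this. It is inferred from the missing date, and all move-ins together come to about 1–2% over a normal recruitment window.

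**Conclusion.** The point holds as a gap in safeguards. Eligible residents are neither fixed before allocation nor expressly all to be approached, the programme is known at approach, and first contact runs through agency staff whose professional group also supplies or reviews the A/CB outcomes. The mix of enrolled residents can therefore differ by arm. The documents do not show that it does, and they give no direction or size.

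The exposed analysis is Aim 3, where incident counts are compared with no stated baseline adjustment. A factor of about 1.1 to 1.2 is plausible there, resting wholly on the assumed enrolment rates and the assumed fivefold incident rate. In Aim 1 the level bias is limited, though selection on motivation or expected response would survive baseline adjustment. The change should be made, but the gap does not invalidate the design.

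**What to change.** Keep consent after randomisation, and change the following.

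- **Homes still to be randomised** (36 − 25 = 11 remain to be recruited, less any whose earlier allocation stands): before allocation, the agency supplies a coded list, without names, of residents meeting criteria (1)–(3) on a fixed date. Everyone on it, or their guardian, is approached, and only listed residents are enrolled.
- **Paused homes whose earlier allocation stands:** make the list at a fixed restart date before re-approach, and report arrivals since randomisation separately. Requiring residence on the original randomisation date could exclude current residents.
- **Homes already begun:** rebuild the counts from agency records where possible.
- **Reporting:** give numbers listed, approached and consenting by arm. Add prior incident counts of non-consenters only if the IRB agrees, in aggregate or coded form.
- **Analysis:** compare baseline A/CBs by arm, and adjust the Aim 3 incident comparison for baseline incidents.

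The cost is protocol and analysis wording, an IRB submission, and a list drawn from records already used for eligibility. A few late arrivals cannot be enrolled. The list and approach rule guard against selective approach; they do not prevent differential consent, but make it measurable.
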